8.3.3 Classification of an Adverse Event

8.3.3.1 Severity of Event

The following guidelines will be used to describe severity of each adverse event:

- **Mild** – Events require minimal or no treatment and do not interfere with the participant’s daily activities.
- **Moderate** – Events result in a low level of inconvenience or concern with the therapeutic measures. Moderate events may cause some interference with functioning.
- **Severe** – Events interrupt a participant’s usual daily activity and may require systemic drug therapy or other treatment. Severe events are usually potentially life-threatening or incapacitating. Of note, the term “severe” does not necessarily equate to “serious”.

8.3.3.2 Relationship to Study Intervention

All adverse events (AEs) must have their relationship to study intervention assessed by the clinician who examines and evaluates the participant based on temporal relationship and his/her clinical judgment. The degree of certainty about causality will be graded using the categories below. In a clinical trial, the study product must always be suspect.

- **Definitely Related** – There is clear evidence to suggest a causal relationship, and other possible contributing factors can be ruled out. The clinical event, including an abnormal laboratory test result, occurs in a plausible time relationship to study intervention administration and cannot be explained by concurrent disease or other drugs or chemicals. The response to withdrawal of the study intervention (dechallenge) should be clinically plausible. The event must be pharmacologically or phenomenologically definitive, with use of a satisfactory rechallenge procedure if necessary.
- **Probably Related** – There is evidence to suggest a causal relationship, and the influence of other factors is unlikely. The clinical event, including an abnormal laboratory test result, occurs within a reasonable time after administration of the study intervention, is unlikely to be attributed to concurrent disease or other drugs or chemicals, and follows a clinically reasonable response on withdrawal (dechallenge). Rechallenge information is not required to fulfill this definition.
- **Potentially Related** – There is some evidence to suggest a causal relationship (e.g., the event occurred within a reasonable time after administration of the trial medication). However, other factors may have contributed to the event (e.g., the participant’s clinical condition, other concomitant events). Although an AE may rate only as “possibly related” soon after discovery, it can be flagged as requiring more information and later be upgraded to “probably related” or “definitely related”, as appropriate.
- **Unlikely to be related** – A clinical event, including an abnormal laboratory test result, whose temporal relationship to study intervention administration makes a causal relationship improbable (e.g., the event did not occur within a reasonable time after administration of the study intervention) and in which other drugs or chemicals or underlying disease provides plausible explanations (e.g., the participant’s clinical condition, other concomitant treatments).
- **Not Related** – The AE is completely independent of study intervention administration, and/or evidence exists that the event is definitely related to another etiology. There must be an alternative, definitive etiology documented by the clinician.

8.3.3.3 Expectedness

The Medical Monitor will be responsible for assessing whether a suspected serious adverse reaction is expected or unexpected. A suspected serious adverse reaction will be considered unexpected if the nature, severity, or frequency of the event is not consistent with the risk information previously described for the study intervention.

8.3.4 Time Period and Frequency for Event Assessment and Follow-Up

The Investigator will record all reportable events with start dates occurring any time after informed consent is obtained until day 31 or the last day of study participation. At each study visit, the investigator will inquire about the occurrence of AE/SAEs since the last visit. Events will be followed for outcome information until resolution or stabilization.

The occurrence of an adverse event (AE) or serious adverse event (SAE) may come to the attention of study personnel during study visits and interviews of a study participant presenting for medical care, or upon review by a study monitor.

All AEs including local and systemic reactions not meeting the criteria for SAEs will be captured on the appropriate case report form (CRF). Information to be collected includes event description, time of onset, clinician's assessment of severity, relationship to study product (assessed only by those with the training and authority to make a diagnosis), and time of resolution/stabilization of the event. All AEs occurring while on study must be documented appropriately regardless of relationship. All AEs will be followed to adequate resolution.

Any medical condition that is present at the time that the participant is screened will be considered as baseline and not reported as an AE. However, if the study participant's condition deteriorates at any time during the study, it will be recorded as an AE.

Changes in the severity of an AE will be documented to allow an assessment of the duration of the event at each level of severity to be performed. AEs characterized as intermittent require documentation of onset and duration of each episode.

8.3.5 Adverse Event Reporting

The investigator must assess the seriousness of each adverse event and record all serious and non-serious adverse events in the case report form (CRF). The investigator must document serious adverse events as thoroughly as possible and provide a definitive medical diagnosis, if possible.

8.3.6 Serious Adverse Event Reporting

The study clinician will immediately report to the sponsor any serious adverse event, whether or not considered study intervention related, including those listed in the protocol or investigator brochure and must include an assessment of whether there is a reasonable possibility that the study intervention caused the event. Study endpoints that are serious adverse events (e.g., all-cause mortality) must be reported in accordance with the protocol unless there is evidence suggesting a causal relationship between the study intervention and the event (e.g., death from anaphylaxis). In that case, the investigator must immediately report the event to the sponsor.

All serious adverse events (SAEs) will be followed until satisfactory resolution or until the site investigator deems the event to be chronic or the participant is stable. Other supporting documentation of the event may be requested by the Data Coordinating Center (DCC) and/or study sponsor and should be provided as soon as possible.

The study sponsor will be responsible for notifying the local competent authorities of any unexpected fatal or life-threatening suspected adverse reaction as soon as possible, but in no case later than 7 calendar days after the sponsor's initial receipt of the information. In addition, the sponsor will notify local competent authorities and all participating investigators of any new potential serious risks, from

clinical trials or any other source, as soon as possible, but in no case later than 15 calendar days after the sponsor determines that the information qualifies for reporting.

8.3.7 Events of Special Interest

As done in usual care, any secondary effect of steroids treatment will be assessed at every visit with a special attention to:

- Active infection
- Thrombo-embolism event
- Fracture
- Gastro-intestinal bleeding

The investigator must notify the sponsor without delay on the day the investigator becomes aware of the following adverse events, in the same manner and within the same deadline as for serious adverse events (see above).

- Thrombo-embolic event
- Gastro-intestinal bleeding

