6.3 MEASURES TO MINIMIZE BIAS: RANDOMIZATION AND BLINDING

The randomization list will be generated by a central statistician. A centralized randomization will be implemented for the study. Patients meeting eligibility criteria will be randomized either to intervention group (usual care + prednisone) or control group (usual care). The randomization will be performed in a 1:1 ratio, stratified by center and block balanced. The block size will not be communicated to the investigators.

This will be an open-label study. No investigator will have access to the randomization scheme during the course of the study.

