8.2 SAFETY AND OTHER ASSESSMENTS

Safety will be assessed at each study visit. In addition to assessment of signs and symptoms during physical examination, safety will be assessed through local laboratory values obtained as standard of care and per protocol. The occurrence of any adverse events will also be elicited through non-directive questioning of the patient at each study visit and through recording of any event spontaneously reported by the patient or noted by the investigator.

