9.4.4 Safety Analyses

Adverse events will be coded using the Medical Dictionary for Regulatory Activities (MedDRA). The incidence of adverse events with an onset after randomization through 30 days post-randomization will be tabulated by system organ class and preferred term. All adverse events, fatal adverse events, serious adverse events will be summarized by treatment group. Treatment-related adverse events are those that are considered by the investigator as potentially, probably, or definitely related to the study intervention.

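### Section 8.3.7 ties the directed check for four harms to steroid effects and does not say that it is made in both arms of this open-label trial

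*Protocol*

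**What the plan says.** Section 8.3.7 sets up a directed check: "As done in usual care, any secondary effect of steroids treatment will be assessed at every visit with a special attention to" four event types, namely active infection, thrombo-embolism, fracture and gastro-intestinal bleeding. No arm is named. For two of the four, thrombo-embolism and gastro-intestinal bleeding, the same section adds fast reporting, this time in neutral terms: "The investigator must notify the sponsor without delay on the day the investigator becomes aware of the following adverse events".

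The general collection of adverse events does not depend on arm. Section 8.2 says: "The occurrence of any adverse events will also be elicited through non-directive questioning of the patient at each study visit". Section 8.3.4 says: "At each study visit, the investigator will inquire about the occurrence of AE/SAEs since the last visit", and also: "All AEs occurring while on study must be documented appropriately regardless of relationship".

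Section 6.3 states the masking: "This will be an open-label study". Section 9.4.4 makes the comparison that these data feed: "All adverse events, fatal adverse events, serious adverse events will be summarized by treatment group". The tabulation covers onsets after randomization through 30 days.

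**The concern.** The object of the directed check is a steroid side effect. A usual-care patient normally has no steroid, so an investigator who takes the sentence at its word may see nothing to assess in that patient. The opening appeal to usual care points the same way, since in ordinary practice steroid side effects are sought in patients who take steroids. The investigator knows the arm at every visit. Section 4.2 defends the open label only for the primary outcome and for clinical outcomes such as death and rehospitalization, on the ground that they are objective. It does not speak to adverse events.

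Other text gives further reason to look harder on prednisone. Section 7.1 lists three of the four event types among the reasons for discontinuing study treatment, which only prednisone patients receive. Section 8.3.3.2 tells the clinician to keep the study product under suspicion when judging causality.

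At stake is the by-arm comparison of the harms on which section 2.3.1 builds its risk assessment. Section 2.3.2 presents the pilot as preparation for phase 3 trials. If the search is uneven, an excess on prednisone may be partly an artefact, and a real excess becomes harder to interpret. An analysis plan cannot repair this, because it cannot recover events that nobody asked about.

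**Working it through.** **Step 1. Does other text equalise the search?** The provisions that apply to both arms are:

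- Section 8.2: open questioning at each visit, plus anything the patient volunteers or the investigator notices. By design this is not directed at named events.
- Section 8.3.4: a general inquiry about adverse events at each visit, and a rule that events are documented whatever their presumed cause. The rule governs the recording of known events. It does not fix how hard they are looked for.
- Section 8.1.2: physical examination, with temperature, at Visits 1 to 5.
- Section 8.1.7: haemoglobin, white cell and lymphocyte counts before randomization, at day 7 and at day 31.

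The last two bear on infection and bleeding and are the same in both arms, so they narrow the possible gap. None of the four provisions is a directed question about the four event types, so the gap is not closed.

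**Step 2. Size under stated assumptions.** The protocol gives no detection probabilities and no figure for ascertainment, so there is none to reproduce. Allocation is equal ("The randomization will be performed in a 1:1 ratio, stratified by center and block balanced"), with 60 patients per group (section 9.2).

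Assume the same true risk r in both arms, full detection on prednisone, and a detection fraction s in controls. Then:

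- expected recorded events: 60 × r on prednisone and 60 × r × s in control;
- apparent risk ratio: r / (r × s) = 1/s;
- spurious risk difference: r × (1 − s).

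| Assumed s | Apparent ratio 1/s | r = 5%: events, difference | r = 10%: events, difference | r = 20%: events, difference |
|---|---|---|---|---|
| 1.0 | 1.00 | 3.0 v 3.0, 0 points | 6.0 v 6.0, 0 points | 12.0 v 12.0, 0 points |
| 0.9 | 1.11 | 3.0 v 2.7, 0.5 points | 6.0 v 5.4, 1 point | 12.0 v 10.8, 2 points |
| 0.8 | 1.25 | 3.0 v 2.4, 1 point | 6.0 v 4.8, 2 points | 12.0 v 9.6, 4 points |
| 0.6 | 1.67 | 3.0 v 1.8, 2 points | 6.0 v 3.6, 4 points | 12.0 v 7.2, 8 points |
| 0.5 | 2.00 | 3.0 v 1.5, 2.5 points | 6.0 v 3.0, 5 points | 12.0 v 6.0, 10 points |

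Both r and s are assumptions. The ratio column restates the assumed s and is not evidence that s is below 1.

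**Step 3. The protocol's own rate.** Sections 2.2 and 2.3.1 put the listed steroid harms (sepsis, thrombo-embolism, fracture, gastro-intestinal bleeding) at under 2 per 1000 patient-years.

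- Follow-up per arm: 60 × 30 / 365.25 = 4.93 patient-years.
- Expected events per arm: at most 4.93 × 0.002 = 0.0099, about 0.01.
- If the rate in acute heart failure were ten times as high (an assumption): about 0.1.

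At such counts, uneven searching for these rarer events would hardly ever show in a table. The rate covers sepsis but not infection in general, so it does not bound the problem for minor infection.

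**The case against.** A reader might infer that the check applies to the prednisone arm only and therefore biases the harm comparison. The documents do not support that. Section 8.3.7 contains no such limit. Its visit schedule is shared by both arms, and its notification rule is worded for adverse events without regard to arm or cause. Where the protocol means one arm only, it says so, as the Schedule of Activities (section 1.3) does for study drug. Section 6.5.3 allows prednisone in controls on a formal indication, so assessing steroid effects there is not meaningless. Nor do controls depend on spontaneous report alone: Step 1 lists inquiry, examination and laboratory tests in both arms. Finally, section 9.4.4 already tabulates all adverse events by arm whatever their cause. All of this stands.

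The objection leaves the core untouched. Silence about arm in a sentence about steroid effects can be read in two ways, and the five sites may not read it alike. Rescue steroids in controls do not help, because the check would then follow steroid exposure rather than randomized arm. Recording rules and by-arm tables act on events already found.

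The objection on size also carries weight. The detection fractions are assumed, and even at a 10% risk, s = 0.8 shifts about one event (6.0 against 4.8).

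**Conclusion.** The point holds as a gap in wording that leaves room for differential ascertainment. It is not a demonstrated bias. It rests on three facts: the only directed check is tied to steroid effects, no sentence extends it to both arms, and the arm is known to the investigator.

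The size cannot be determined from the document. Assumed detection fractions of 0.9 to 0.5 give apparent ratios of 1.11 to 2.00 under no true difference. The exposure is mainly in minor infection and minor bleeding, where detection depends on asking. Deaths and events leading to hospitalization are little affected, and for the rarer events the protocol's own rate implies almost no observable counts. Severity is minor; the change is worth making because it is nearly free.

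**What to change.** Reword section 8.3.7 along these lines: *At each of Visits 2 to 5, the investigator will ask every randomized patient, in the same way in both treatment groups, about active infection, thrombo-embolic event, fracture and gastro-intestinal bleeding since the previous visit, and will record the answers whatever the suspected relation to steroids.*

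Visit 1 is left out because section 8.3.4 treats conditions present at screening as baseline. Visit 5 is the last because routine adverse event collection runs to day 31.

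Report the four event types by randomized arm within the adverse event summaries that section 9.4.4 already plans. No new analysis is needed.

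The cost is one reworded sentence, a few CRF items at existing visits and slightly more site time, chiefly for control patients. No dose, treatment rule or visit changes. Patients already seen before the change would have been questioned under the present wording, and the report should say so.

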8.3.8 Reporting of Pregnancy

Any pregnancy that occurs following randomization through Day 31 should be reported to the Medical Monitor and to the Sponsor.

9 STATISTICAL CONSIDERATIONS

9.1 STATISTICAL HYPOTHESES

The primary statistical null hypothesis to be tested is that the mean change in CRP from inclusion to day 7 does not differ between patients randomized to prednisone therapy and those randomized to usual care. The alternative hypothesis is that the mean change in the two groups differ. Two-sided $p < 0.05$ will be considered statistically significant, with a greater CRP reduction in the investigational arm considered superior.

9.2 SAMPLE SIZE DETERMINATION

Raess et al (2021) observed a 58% lower day 7 CRP level in patients with community-acquired pneumonia treated with 7 days of 50 mg/day prednisone (geometric mean 14.71, geom SD 2.47) than with placebo (geom mean 34.84, geom SD 2.98). Baseline CRP levels were similar in the two groups with geometric means (SDs) of 121.57 (2.77) and 124.58 (2.70) mg/L, in the active and placebo treatment groups respectively.

Sixty patients per group provides approximately 80% power to detect a 40% lower day 7 CRP level in the intervention (prednisone + routine care) group than in the control (routine care) group at the 2-sided 0.05 significance level assuming a common geometric standard deviation of 2.7237 (SD of logs 1.002). Power was estimated using a t-test, although groups will be compared with respect to the day 7 CRP level using MMRM as described below. CRP values will be log-transformed for analysis.

9.3 POPULATIONS FOR ANALYSES

Since the trial is a small pilot study, and a few inappropriately enrolled or treated patients can have a major effect on the findings, the main analysis will be performed in the per-protocol population. Sensitivity analyses on the main endpoint will be performed considering the intention-to-treat population.

Intention to treat population (ITT): all randomized patients, excluding patients randomized in error (e.g., non-existent patients or patients randomized and found to be ineligible before study treatment started) regardless of the strategy received by the patient. Patients will be analyzed according to the treatment to which they were assigned at randomization.

The per-protocol (PP) population is defined as all patients randomized (excluding patients randomized in error), without major protocol violations/deviations. Pre-defined major protocol violations/deviations are:

- Non-respect of eligibility criteria
- Non-respect of the allocated treatment

Major protocol deviation will be classified during a data review before final data base lock.

In case of consent withdrawal, only data collected before withdrawal will be used.

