7.2 PARTICIPANT DISCONTINUATION/WITHDRAWAL FROM THE STUDY

- Participants may exit the study at any time and for any reason.
- The investigator can temporarily or permanently withdraw a participant from the study for any safety reason or if it is in the participant's best interests.

If a participant withdraws consent, any data collected prior to the date of premature exit may still be used.

Participants are free to withdraw from participation in the study at any time upon request. The patient should be considered to have withdrawn consent only when the patient has withdrawn consent to further participate in any aspect of the study, including any further visits, assessments, or study-related contacts. If a patient fully withdraws consent, the investigator must make every effort to determine the primary reason for this decision and record this information. The study intervention must be discontinued and no further assessments conducted. Information collected prior to withdrawal from the study will still be used. Information that has already been sent to the study Sponsor cannot be withdrawn. All biological material that has not been analyzed at the time of withdrawal must not be used. If the participant requests, previously retained samples will be destroyed to prevent further analysis. Further attempts to contact the patient are not allowed unless safety findings require communicating or follow-up. However, if local regulations permit, the investigator will be asked to check public registries on a regular basis to obtain the survival status (dead or alive) of any patients who failed to complete the study.

In case of serious adverse events, see the corresponding section 8.3.6 for reporting requirements.

If a participant discontinues the study, this will in no way affect their usual care for their condition. In the event of serious adverse events following premature discontinuation of treatment see section 7.1.

Patients who are randomized in error may be withdrawn from the study and replaced (with assignment of new study identification number and new randomization). Patients randomized in error will not be included in the analyses.

Patients who are randomized and then withdraw or are withdrawn from the study will not be replaced. These patients will be included in analyses. Incomplete follow-up will be handled as censored observations in time-to-event analyses, and missing data will be handled through imputation as appropriate.

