8.1.6 Other clinical outcomes

Deaths will be recorded through 90 days post-randomization. The primary cause will be recorded when possible. Every effort (consistent with all applicable laws and regulations) will be made to obtain vital status on all randomized subjects.

The length of stay in an intensive care unit (ICU) or other acute care unit and the total length of hospital stay will be recorded for the initial hospitalization and of each rehospitalization through 90 days following randomization. The primary reason for the readmission to the hospital will be recorded. A rehospitalization is defined as an unplanned overnight stay in the hospital, regardless of whether the patient was admitted.

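### Section 9.3 admits only pre-withdrawal data, while Sections 7.2 and 8.1.6 seek vital status after withdrawal; read literally, it drops that status from all-cause mortality at days 31 and 91 (minor)

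*Protocol*

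**What the plan says.** Four parts of the protocol bear on this.

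- **Section 9.3 (Populations for Analyses)** sets the rule for use: "In case of consent withdrawal, only data collected before withdrawal will be used". It makes no exception for vital status.
- **Section 7.2 (Participant Discontinuation/Withdrawal)**, in its paragraph on full withdrawal of consent, ends assessments and generally ends contact. It then adds an exception, opening with "However, if local regulations permit", under which "the investigator will be asked to check public registries on a regular basis to obtain the survival status (dead or alive) of any patients" who did not complete the study. On earlier data it says "Information collected prior to withdrawal from the study will still be used", which permits use of those data without confining use to them. It also keeps withdrawn patients in the analyses, with incomplete follow-up censored.
- **Section 8.1.6 (Other clinical outcomes)** states "Deaths will be recorded through 90 days post-randomization" and "Every effort (consistent with all applicable laws and regulations) will be made to obtain vital status on all randomized subjects".
- **Sections 9.4.3 and 9.4.9** use the data. All-cause death is a component of the first secondary endpoint (WHF adverse event, HF readmission or death through day 91), and is an exploratory endpoint in its own right at days 31 and 91.

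**The concern.** The protocol asks sites to obtain a piece of information and then forbids the analyst to use it. If a withdrawn patient is found in a registry to have died on, say, day 60, Sections 7.2 and 8.1.6 treat that as information the trial wants, while Section 9.3 requires the patient to be analysed as if nothing were known after withdrawal.

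The endpoint directly at stake is all-cause mortality at days 31 and 91. Vital status is the one outcome that can be completed without the patient's further participation, and completing it spares the analysis from assuming that censoring at withdrawal is unrelated to prognosis. There is also a consent aspect: looking up the survival of people who have withdrawn is hard to justify if the analysis may not use the result.

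**Working it through.** **Setting the sections side by side**

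1. Does the registry check cover patients who withdrew consent? Yes. It stands in the paragraph on full withdrawal, directly after the bar on further contact, and is worded as an exception to it.
2. Does 8.1.6 cover them? By its terms, yes: the effort "will be made to obtain vital status on all randomized subjects" leaves out no group, though it is bounded by applicable law.
3. Does 9.3 allow use of the result? Not as written. Registry status found after withdrawal is not data collected before withdrawal, and the word *only* closes the list.
4. Does another section restore it? No. Section 7.2 permits use of earlier data but is silent on using the registry result.

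The conflict is therefore in the stated text and does not depend on something left unsaid.

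**Which endpoints are affected**

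- CRP change at day 7: none. A registry supplies no CRP value.
- All-cause mortality at days 31 and 91: directly affected, since registry status is a complete observation of this endpoint.
- First secondary composite: only partly informed. A registry shows death, but not a WHF adverse event or an HF readmission. Extending follow-up to the registry date would count event-free time during which two of the three components could not be seen.

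**Size**

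The protocol gives no figure for this point to reproduce. The expected number of deaths set aside is

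E = N × w × m,

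and the chance of at least one is 1 − (1 − m)^(N × w), where

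- N = 120 (Sections 1.1 and 5.5);
- w = proportion withdrawing consent, not in the protocol, assumed 3% to 5%, so N × w = 120 × 0.03 = 3.6 to 120 × 0.05 = 6 patients;
- m = mortality among them, taken from the protocol's background 1-month figures: 6% overall (Section 2.1) and 10% in older patients (Sections 2.2 and 2.3.2).

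| Withdrawn | m | E | Chance of at least one |
|---|---|---|---|
| 3.6 | 6% | 3.6 × 0.06 = 0.22 | 1 − 0.94^3.6 = 20% |
| 3.6 | 10% | 3.6 × 0.10 = 0.36 | 1 − 0.90^3.6 = 32% |
| 6 | 6% | 6 × 0.06 = 0.36 | 1 − 0.94^6 = 31% |
| 6 | 10% | 6 × 0.10 = 0.60 | 1 − 0.90^6 = 47% |

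At the same rates the whole trial would see 120 × 0.06 = 7.2 to 120 × 0.10 = 12 deaths by day 31. The upper end treats all 120 patients as older, although eligibility runs from 18 to 85 years.

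The affected window runs to day 91, for which the protocol states no mortality. As a wider sensitivity range resting wholly on assumption, w of 2% to 10% and m of 6% to 20% give E from 2.4 × 0.06 = 0.14 to 12 × 0.20 = 2.4.

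All these values count every death among withdrawn patients as found in a registry, so incomplete or unavailable registries would lower them.

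**The case against.** The strongest reply is that little turns on this and that a route to settle it exists. Section 9.4.1 says a SAP will be written before database lock and will prevail over the protocol's planned analyses. That SAP is not shown and may already deal with the matter. The registry check also operates only where local regulations permit, so it is unknown whether any such status would be obtained at the five Armenian sites. One can also read 9.3 as meant for study assessments rather than public records. These points keep the matter small. They do not remove it: 9.3 draws no such distinction, and a SAP that used registry deaths would be departing from an express protocol rule on data after consent withdrawal.

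Several stronger readings are tempting, and the protocol does not support them.

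- *That the main secondary composite is compromised.* Registries cannot show two of its three components, so censoring at withdrawal is a defensible main analysis, and it is what 9.3 already yields.
- *That 8% to 14% of early deaths would be lost.* Those are the shares of a single death among 12 or 7.2 (1/12 and 1/7.2). They are not an expected loss, which is below one death under the 3% to 5% assumption.
- *That the censoring rule in 9.4.3 is a second contradiction.* Its reference to the last follow-up on hand is open to two readings only if 9.3 is first set aside. If 9.3 governs, data stop at withdrawal.
- *That the choice would be made at data review with outcomes and allocation known.* The review described in 9.3 classifies major protocol deviations. Nothing assigns withdrawal data to it.
- *That withdrawals will differ by arm or be sicker.* This is possible in an open-label trial, but the protocol gives no evidence for it.

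**Conclusion.** The inconsistency is real and can be verified from the text. As written, 9.3 excludes lawfully obtained post-withdrawal vital status from all-cause mortality at days 31 and 91, while 7.2 and 8.1.6 seek it. The severity is minor. The primary endpoint is untouched, the main composite analysis need not change, and the expected effect is about 0.2 to 0.6 deaths. That size rests on an assumed 3% to 5% withdrawal and on background 1-month mortality of 6% to 10%, the upper figure applying to older patients only. It cannot be made firmer, because the protocol states neither a withdrawal rate nor a 90-day mortality.

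**What to change.** Extend the sentence in 9.3 so that it reads "In case of consent withdrawal, only data collected before withdrawal will be used", followed by: except vital status obtained from public registries where local regulations permit (7.2).

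Then state how that status is used:

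- **All-cause mortality to days 31 and 91:** use it for every withdrawn patient for whom it is obtained, taking both dates of death and last-known-alive dates. Adding deaths while leaving survivors censored at withdrawal would count events without the matching time at risk.
- **Composite endpoint:** keep censoring at withdrawal in the main analysis. Add registry deaths, with matching follow-up time for survivors, in a sensitivity analysis.

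The cost is one clause, one extra sensitivity run and the usual approval of a protocol change. Sites are already asked for the data. What becomes available will still depend on local registry rules.
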